### 1.1. Trial Objectives

See CTP, Section 2.1.

### 1.2. Trial Design

See CTP, Section 3.1.

### 1.3. Statistical Hypotheses for Trial Objectives

No formal statistical hypothesis will be tested.

### 1.4. Sample Size Justification

See CTP, Section 11.2.

### 1.5. Randomization and Blinding

See CTP, Section 5.

## 2. GENERAL ANALYSIS DEFINITIONS

A baseline (or reference) value will be defined as the value of the last available assessment performed prior to the first dose (active vaccine or placebo).

### 2.1. Analysis Windows

The phases and periods in the study will be constructed as follows:

**Table 3: Phase and Period Definitions**

Phase	Phase number	Period	Period number	Interval	
				From	To
Screening	1			00:00 of the date of signing the informed consent form a	One minute prior to Dose 1 on Day 1
Regimen	2	Post-Dose 1	1	Date and time of Dose 1 (Day 1)	Minimum of: 
 
a) Maximum (28 days after first vaccination at 23:59, scheduled visit 4 weeks after first vaccination at 23:59)
 
b) 23:59 at the date of last contact (for early discontinuation)
 

Follow-Up 1	3			1 minute after end of Post-Dose 1 period	Minimum of: 
 
a) One minute prior to date and time of the next vaccination
 
b) 23:59 at the date of last contact (for early discontinuation)
 

Regimen	2	Post-Dose 2	2	Date and time of Dose 2 (Day 85)	Minimum of: 
 
a) Maximum (28 days after second vaccination at 23:59, scheduled visit 4 weeks after second vaccination at 23:59)
 

Phase	Phase number	Period	Period number	Interval	
				From	To
					b) 23:59 at the date of last contact (for early discontinuation) c) One minute prior to post-dose 3
Follow-Up 2	4			1 minute after end of Post-Dose 2 period	Minimum of: a) One minute prior to date and time of the next vaccination b) 23:59 at the date of last contact (for early discontinuation)
Regimen	2	Post-Dose 3	3	Minimum of Date and Time of the two Dose 3 Injections (Day 169)	Minimum of: a) Maximum (28 days after third vaccination at 23:59, scheduled visit 4 weeks after third vaccination at 23:59) b) 23:59 at the date of last contact (for early discontinuation)
Follow-Up 3	5			1 minute after end of Post-Dose 3 period	Minimum of: a) One minute prior to date and time of the next vaccination b) 23:59 at the date of database cut-off c in case of interim c) 23:59 at the date of last contact (for early discontinuation)
Regimen	2	Post-Dose 4	4	Minimum of Date and Time of the two Dose 4 Injections (Day 337)	Minimum of: a) Maximum (28 days after fourth vaccination at 23:59, scheduled visit 4 weeks after fourth vaccination at 23:59) b) 23:59 at the date of database cut-off c in case of interim c) 23:59 at the date of last contact (for early discontinuation)
Follow-Up 4	6			1 minute after end of Post-Dose 4 period	Minimum of: a) Last available visit for completers c b) 23:59 at the date of last contact (for early discontinuation) c

## NOTE:

a The start time of screening phase is 00:00. In case an earlier date is available (e.g. for lab or vital signs then use the very first date in order to include all data)

b In case a dose is not administered, the observations end up in the previous Follow-Up phase

c This timepoint is intended to be at the end of the main study i.e. Week 96, cut-off used is 29AUG2017. LTE data will be reported separately

For the immunogenicity analyses no phases will be constructed.

The periods/phases will be used primarily for safety and concomitant medication allocation. The post-dose periods (and the regimen phase) are considered active periods/phase, the screening and follow-up phases are considered non-active phases. There will be no phase defined for the LTE part of the study.

For descriptive statistics over time, assessments (regardless of the investigated parameter) will be allocated to an analysis visit based on the visit number as captured in the database.

For subjects that received a first dose, but did not receive a 2nd dose while still continuing their planned visit schedule, the measurements after the planned but not administered 2nd dose will not be included in graphs and tables showing descriptive statistics over time. Those measurements will be shown in listings but it will be indicated that these are not used in the analysis. Moreover, the vaccinations done after a missed one will be not be shifted to the previous one but will be considered as planned: in the example above if the 2nd is missed, the 3rd vaccination will still be reported as post-dose 3.

## 2.2. Pooling Algorithm for Analysis Centers

Not planned, subgroups analyses by region are described in section 2.4.

## 2.3. Analysis Sets

### 2.3.1. Full Analysis Set

The Full Analysis Set (FA) will consist of all subjects who were randomized and who received at least one dose of study vaccine. This will be the primary population for all analyses (except immunogenicity, see below) described in this document.

### 2.3.2. Per-Protocol Immunogenicity Analysis Set

The per protocol immunogenicity (PPI) population consist of all subjects who have received at least the first three vaccinations, according to the protocol-specified vaccination schedule (+/- 2 weeks), have at least one measured post-dose blood sample collected and were not diagnosed with HIV during the study. Samples taken after Week 48 from subjects in the PPI population who missed the 4th vaccination or did not receive the 4th vaccination in the protocol-specified time window (+/- 2 weeks) will be excluded from the analysis.

The analysis of the immune responses will be performed on the per protocol immunogenicity population.

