11.1. Analysis Populations

The safety population will consist of all subjects who received at least one dose of study vaccine, and for whom any post-dose data is available.

The immunogenicity population will consist of all subjects who received at least one dose of study vaccine, and who have data from at least one post-dose blood sample.

The per-protocol population will consist of all subjects who have received at least the first three vaccinations according to the protocol-specified vaccination schedule, have at least one measured post-dose blood sample collected, and who have no major protocol violations impacting immunogenicity assessments.

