11.4. Immunogenicity Analyses

No formal hypothesis on immunogenicity will be tested. The analysis of immunogenicity will be done on the immunogenicity and per-protocol populations as defined in Section 11.1.

Descriptive statistics (actual values and changes from reference) will be calculated for continuous immunologic parameters at all time points. Graphical representations of changes in immunologic parameters will be made as applicable. Differences between groups at a specific time point will be tested for exploratory purposes by a 2-sample t-test if the data appear to be normally distributed. If not, the non-parametric Wilcoxon rank sum test will be used. If portions of the measurements are censored below the assay quantification limit, the Gehan-Wilcoxon test will be employed. All statistical tests will be two-sided and will be considered statistically significant if $p<0.05$.

Frequency tabulations will be calculated for discrete (qualitative) immunologic parameters at all time points. Significant differences between groups will be determined by a 2-sided Fisher's exact test.

Magnitude and breadth of (neutralizing) antibody responses will be explored graphically through the generation of individual magnitude-breadth (M-B) curves. The area under the M-B curve (AUC) provides an overall summary of the M-B profile. The AUCs will be compared between groups using the Wilcoxon-Mann-Whitney test.

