### 2.3.1. LTE Analysis Set

The Long Term Extension (LTE) population consists of all subjects in the Per-Protocol Immunogenicity Analysis Set, randomized in group 1 or 2 who had at least one visits in the long term extension part of the study.

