## 6. IMMUNOGENICITY

### 6.1. Analysis specifications

The analysis of immunogenicity will be done on the PPI analysis set (Section 2.3).

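### The SAP plans all immune-response results on its PPI set alone, leaves out the protocol's immunogenicity population without a reason, and defines PPI differently from the protocol's per-protocol set

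*SAP*

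**What the plan says.** Protocol 11.4 states: "The analysis of immunogenicity will be done on the immunogenicity and per-protocol populations as defined in Section 11.1". Protocol 11.1 defines the wider set as follows: "The immunogenicity population will consist of all subjects who received at least one dose of study vaccine", provided that data exist from at least one post-dose sample. Its per-protocol set needs the first three vaccinations on schedule and a post-dose sample, and is limited to subjects "who have no major protocol violations impacting immunogenicity assessments".

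The SAP defines three sets: Full Analysis, PPI and LTE. On the Full Analysis Set it says: "This will be the primary population for all analyses (except immunogenicity, see below) described in this document". Sections 2.3.2 and 6.1 both send immunogenicity to PPI: "The analysis of the immune responses will be performed on the per protocol immunogenicity population". The LTE set "consists of all subjects in the Per-Protocol Immunogenicity Analysis Set, randomized in group 1 or 2". The protocol's immunogenicity population appears nowhere in the SAP, and neither the amendment history nor the introduction explains its absence.

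PPI requires the first three doses on schedule with a 2-week tolerance, one post-dose sample, and that subjects "were not diagnosed with HIV during the study". A missed or out-of-window fourth dose removes only samples after Week 48. The introduction adds that the Week 96 analysis has been performed and will not be rerun.

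**The concern.** Comparing Env binding antibody responses between regimens is a primary objective (Protocol 2.1). PPI membership depends on events after randomization: doses received, their timing, and HIV diagnosis. The protocol's second population lets a reader see whether results depend on such exclusions. With PPI alone, that check is lost for the regimen comparison and for durability in Groups 1 and 2.

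The HIV rule has a further problem. It acts on the whole subject, so a late diagnosis discards samples taken while the subject was still testing negative. Protocol 12.3.3 keeps infected subjects in follow-up for immunogenicity, so the data are collected but not used. The same SAP section treats a fourth-dose failure at sample level, which shows that a sample-level rule was available.

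The SAP does tabulate doses in and out of window (4.4), list major deviations (4.5) and tabulate HIV infections (5.1.2). It plans no count of who is excluded from PPI, by group and reason.

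**Working it through.** **The plan's own figure.** Protocol 11.2 describes the immunogenicity population and then gives 45 evaluable subjects per group for a 2.3-fold difference with 80% power (two-sided 5%, SD 0.6 on the log10 scale).
- δ = log10(2.3) = 0.3617.
- n = 2(1.960 + 0.842)² × 0.6² / 0.3617² = 43.2, so 44 per group.
- Power at n = 45 is 81.6% (80.7% by noncentral t). The figure reproduces.
- The 10% allowance (50 to 45) is stated for dropout. No separate allowance is given for off-schedule doses or HIV diagnosis. By the same normal formula, power would be 78.9% at 42 and 76.9% at 40 evaluable per group. These are illustrations only, because the documents give no PPI counts.

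**The three definitions side by side.**

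| Criterion | Protocol immunogenicity population | Protocol per-protocol set | SAP PPI |
|---|---|---|---|
| Doses | At least one | First three, on schedule | First three, on schedule with 2-week tolerance |
| Post-dose sample | At least one | At least one | At least one |
| Major violations affecting immunogenicity | Kept | Excluded | No criterion |
| HIV diagnosis during the study | Kept | No criterion | Whole subject excluded |
| Fourth dose missed or out of window | Kept | No criterion | Samples after Week 48 excluded |

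Omitting the violation criterion widens PPI relative to the protocol's per-protocol set, while the HIV rule narrows it. The net effect on any group cannot be derived from the documents.

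**Loss per HIV-diagnosed subject.** Inputs:
- HIV tests at Weeks 24, 48, 78, 96 and each LTE visit (Protocol 9.3.2).
- LTE visits at Weeks 120 to 336 in steps of 24 (Protocol 9.1.2): (336 − 120)/24 + 1 = 10.
- Post-dose Env ELISA timepoints at Weeks 28, 52, 78 and 96 (SAP 6.5).

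| First positive | Last negative | ELISA timepoints up to last negative | Kept in PPI |
|---|---|---|---|
| Week 48 | Week 24 | 0 | 0 |
| Week 78 | Week 48 | 1 (Week 28) | 0 |
| Week 96 | Week 78 | 3 (Weeks 28, 52, 78) | 0 |
| Week 120 | Week 96 | 4 | 0 |
| Week 336 | Week 312 | 4 + 9 = 13 | 0 |

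Counts above 4 assume Env ELISA at every LTE visit. SAP 6.5 lists Env ELISA only to Week 96, and Protocol 9.2.2 makes it a possible LTE assay, not a fixed one.

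**What the LTE can still change.** LTE entry requires all four vaccinations (Protocol 9.1.8). Among LTE participants, PPI and the protocol's immunogenicity population can therefore differ only through dose timing or HIV diagnosis.

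**The case against.** The strongest reply is that little is at stake. No formal hypothesis is tested, the summaries are descriptive, and the Week 96 analysis is complete. What remains is mainly LTE durability in Groups 1 and 2, which is an exploratory objective. LTE participants had four doses and were selected as low risk for HIV, so the sets should be close. Protocol 11 leaves details to the SAP, major deviations are still listed, and SAP 4.3 flags glucocorticosteroids for possible influence on immunogenicity.

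Most of this stands as a limit on consequence. It does not explain the omission: dropping one of two named populations is more than a detail, and listing deviations does not show results with and without the subjects concerned.

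Four stronger readings are tempting but unsupported.
- A reader might infer that the Week 28 regimen choice rested on a selected population. The documents do not show which set that analysis used. SAP V1.0 and any Week 28 plan are not among them, so results on the wider set may exist.
- A reader might infer from the dates (sponsor unblinded at Week 28, SAP V1.0 in May 2018) that the population was narrowed after seeing data. When the choice was first made is not shown.
- A reader might infer a bias in favour of the vaccine regimens. The two departures work in opposite directions, and no counts are given.
- A reader might take the 2-week tolerance as contradicting the protocol's −1/+3 week windows. SAP 4.4 supports reading it as an extension of those windows, which excludes no on-schedule dose.

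**Conclusion.** The mismatch is certain from the text: the protocol names two populations, the SAP uses one, that one is not the protocol's per-protocol set, and no reason is given. This should be corrected, but it does not invalidate the planned results, and PPI can remain the main set.

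The number of subjects affected and the direction of any bias are unknown. The measurable part is the per-subject loss under the HIV rule: 0, 1, 3 or 4 ELISA timepoints for a first positive at Week 48, 78, 96 or 120, with larger counts conditional on LTE assays. Diagnoses first made in the LTE affect only outputs run after the Week 96 analysis. If V1.0 used the same PPI definition, which cannot be checked, a subject first diagnosed in the LTE would be in the Week 96 outputs but absent from the final PPI and LTE sets.

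**What to change.** 1. Add supplementary Env ELISA tables (Week 28, Week 52, durability, and LTE where assayed) on the protocol's immunogenicity population. Label them as added after unblinding and after the Week 96 analysis, and keep PPI as run. The missed-second-dose rule in SAP 2.1 should not apply to these tables, or it would take out samples that this set is meant to include.
2. Show that wider set both as Protocol 11.1 defines it and with samples after the last negative HIV test removed, so that infection-induced antibody is not mistaken for vaccine response. In PPI, apply the same sample-level rule as a sensitivity in place of the subject-level exclusion.
3. Tabulate PPI exclusions by group and reason.
4. Restore the major-violation criterion, or document why it was dropped.

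The cost is SAP wording, a further run of existing table programs with another population flag, some programming for date-based sample removal and the missed-dose rule, and one exclusions table. The Week 96 analysis is not redone. The added tables are post hoc, and the wider set includes incompletely vaccinated subjects, so its geometric means may be somewhat lower.

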### 2.3.1. LTE Analysis Set

The Long Term Extension (LTE) population consists of all subjects in the Per-Protocol Immunogenicity Analysis Set, randomized in group 1 or 2 who had at least one visits in the long term extension part of the study.

## 2.4. Definition of Subgroups

The following subgroups will be investigated for safety (AE, Lab):

- Sex (Female, Male)
- Race (Caucasian, Black or African American, Asian, Othera)
- Region (East Africa, South Africa, Thailand, USA)
- BMI [<25; 25-<30; ≥30]
- 

The following subgroups will be investigated for immunogenicity:

- Region (East Africa, South Africa, Thailand, USA)
- AD26 VNA at baseline (<LLOQ, >=LLOQ)

The following subgroups will be investigated for the social impact questionnaire:

- Region (East Africa, South Africa, Thailand, USA)
- Sex (Female, Male)

---

a Subgroup “Other” should contain all remaining categories: Other, Multiple, American Indian or Alaska Native, etc.

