- To explore immune responses to the different vaccine regimens in mucosal secretions in a subset of subjects.
- To explore gene expression patterns between the different vaccine regimens.
- To explore neutralization antibodies against the Ad26 vector.
- To assess the social impact of participation in an HIV vaccine study for subjects via a social impact questionnaire.
- To explore durability of the vaccine regimen in the groups selected for the long-term extension phase.

Hypothesis

No formal statistical hypothesis will be tested. This study will evaluate whether a prime/boost vaccine regimen consisting of Ad26.Mos.HIV with or without gp140 protein plus aluminum phosphate adjuvant, or Ad26.Mos.HIV/MVA-Mosaic with or without gp140 protein plus aluminum phosphate adjuvant is safe, well-tolerated and immunogenic, providing broad, functional and durable humoral and cellular responses.

OVERVIEW OF STUDY DESIGN

This is a multicenter, randomized, parallel group, placebo-controlled, double-blind clinical study in healthy HIV-uninfected adult men and women. Subjects will be enrolled regardless of their baseline Ad26 seropositivity, as data from Study IPCAVD003 suggest that there is little impact of baseline Ad26 neutralizing antibodies (nAbs) on the immunogenicity of this Ad26 vaccine vector, at the titers observed in that study, however regional differences are known to occur. Vaccinations are administered as shown in [Table 1](#).

The study comprises a maximum 4-week screening period, a 48-week vaccination period during which subjects will be vaccinated at baseline, Week 12 and Week 24, with a booster at Week 48, and a 48-week follow-up period to the final visit at Week 96. Based on the analysis of the Week 28 data, a Long Term Extension (LTE) phase (approximately 5 years after Week 96) will be performed for subjects randomized to Group 1 and Group 2 and having received all 4 vaccinations. These 2 groups (including a gp140 250 mcg and a gp140 50 mcg dose, respectively) form the basis for the regimens that will be evaluated in future studies. The end of the study will be the last subject's last visit.

Table 1: Study Design HIV-V-A004

| Group | N | Week 0 (baseline) | Week 12 | Week 24 | Week 48 |
|----------|----|----------------------|--------------|---|---|
| Group 1* | 50 | Ad26.Mos.HIV | Ad26.Mos.HIV | Ad26.Mos.HIV + gp140 DP (250 mcg + adjuvant) ^a | Ad26.Mos.HIV + gp140 DP (250 mcg + adjuvant) ^a |

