In IPCAVD003, 24 HIV-1 negative subjects were randomized 3:1 to receive a single vaccination with Ad26.ENVA.01 or placebo. Eight of the subjects were Ad26 seropositive at enrollment. The T-cell responses by ELISPOT were slightly lower in the baseline Ad26 seropositive subjects, the intracellular cytokine staining (ICS) and enzyme-linked immunosorbent assay (ELISA) responses proved comparable between subjects who were Ad26 seropositive and Ad26 seronegative at baseline, both in peripheral blood and in colorectal mucosa. In addition, systemic and mucosal responses persisted for at least 1 year in the majority of subjects after a single IM vaccine dose. These data suggest that the impact of baseline Ad26 nAbs, at the titers observed in that study, on the immunogenicity of this Ad26 vaccine vector is modest. Additionally, there were no consistent increases in Ad26-specific CD4+ T-lymphocyte responses at mucosal surfaces following vaccination in either Ad26 seronegative or Ad26 seropositive subjects.

In this study (HIV-V-A004), Ad26 with mosaic inserts will be used for the first time in a clinical study. It is not expected that the DNA insert will alter the safety of the viral vector. However, an internal Protocol Safety Review Team (PSRT) and an independent data monitoring committee (DMC) will be established and pauses in enrollment, regular safety reviews, and stringent vaccine/study pause rules will be included (see Section 11.9).

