3. STUDY DESIGN AND RATIONALE

3.1. Overview of Study Design

This is a multicenter, randomized, parallel group, placebo-controlled, double-blind clinical study in healthy HIV-uninfected adult men and women. A target of 400 subjects will participate in this study, with 50 subjects planned in each one of eight groups. Subjects will be enrolled regardless

of their baseline Ad26 seropositivity. Randomization will be stratified by region (US, Africa, and Asia). Efforts will be made to enroll a minimum of 50 subjects per region.

Subjects will receive four doses of study vaccine: Ad26.Mos.HIV or placebo will be given at Weeks 0 and 12; Ad.26.Mos.HIV or MVA-Mosaic (both with or without gp140 DP [low or high dose]), gp140 DP (high dose) or placebo will be given at Weeks 24 and 48, as shown in [Table 4](#).

Table 4: Study Design HIV-V-A004

| Group | N | Week 0 (baseline) | Week 12 | Week 24 | Week 48 |
|----------|----|----------------------|--------------|---|---|
| Group 1* | 50 | Ad26.Mos.HIV | Ad26.Mos.HIV | Ad26.Mos.HIV + gp140 DP (250 mcg + adjuvant) ^a | Ad26.Mos.HIV + gp140 DP (250 mcg + adjuvant) ^a |
| Group 2* | 50 | Ad26.Mos.HIV | Ad26.Mos.HIV | Ad26.Mos.HIV + gp140 DP (50 mcg + adjuvant) ^a | Ad26.Mos.HIV + gp140 DP (50 mcg + adjuvant) ^a |
| Group 3 | 50 | Ad26.Mos.HIV | Ad26.Mos.HIV | Ad26.Mos.HIV + Placebo | Ad26.Mos.HIV + Placebo |
| Group 4 | 50 | Ad26.Mos.HIV | Ad26.Mos.HIV | MVA-Mosaic + gp140 DP (250 mcg + adjuvant) ^a | MVA-Mosaic + gp140 DP (250 mcg + adjuvant) ^a |
| Group 5 | 50 | Ad26.Mos.HIV | Ad26.Mos.HIV | MVA-Mosaic + gp140 DP (50 mcg + adjuvant) ^a | MVA-Mosaic + gp140 DP (50 mcg + adjuvant) ^a |
| Group 6 | 50 | Ad26.Mos.HIV | Ad26.Mos.HIV | MVA-Mosaic + Placebo | MVA-Mosaic + Placebo |
| Group 7 | 50 | Ad26.Mos.HIV | Ad26.Mos.HIV | gp140 DP (250 mcg + adjuvant) ^a + Placebo | gp140 DP (250 mcg + adjuvant) ^a + Placebo |
| Group 8 | 50 | Placebo | Placebo | Placebo + Placebo | Placebo + Placebo |

^a Aluminum content will be 0.425 mg/0.5 mL dose

50 mcg and 250 mcg refer to total protein content

Sterilized aluminum phosphate wet gel suspension will be used as adjuvant for gp140 DP

* An optional LTE phase (approximately 5 years) will be performed for subjects randomized to Group 1 and Group 2 and having received all 4 vaccinations

An internal PSRT and an independent DMC will be established for this study. Refer to Sections [11.7](#) and [11.8](#), respectively, for details.

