5. VACCINE ALLOCATION AND BLINDING

Study Vaccine Allocation

Procedures for Randomization

Central randomization will be implemented in this study. Subjects will be randomly assigned to one of eight treatment groups based on a computer-generated randomization schedule prepared before the study by or under the supervision of the sponsor. The randomization will be balanced by using randomly permuted blocks and stratified by region (US, Africa, and Asia). Efforts will be made to enroll a minimum of 50 subjects from each region.

The interactive web response system (IWRS) will assign a unique treatment code, which will dictate the treatment assignment and matching study vaccine for the subject. The requestor must use his or her own user identification and personal identification number when contacting the IWRS, and will then give the relevant subject details to uniquely identify the subject.

Blinding

The subjects, clinical staff, and investigator, will be blinded to study vaccine allocation until Week 96. The sponsor will be blinded to study vaccine allocation until the Week 28 analysis (see Section 11.6). The pharmacist with primary responsibility for vaccine dispensing will not be blinded to the study vaccine.

A pharmacist will prepare study vaccine for administration and will provide it to the clinic. In order to preserve blinding, he/she will place an overlay on the syringes. Administration of study vaccine to the subjects can be performed by a qualified healthcare provider from the study site (including the pharmacist who prepared the study vaccine) who will have, on the day of administration, no other study function related to safety, study data evaluation or recording of AEs for those subjects that he/she vaccinated on that day. More information and details on the preparation of vaccine and adjuvant components, as well as details on the holding time and storage conditions from the time of preparation to delivery of the study vaccine, are provided in Section 14.

The investigator will not be provided with randomization codes. The codes will be maintained within the interactive web response system (IWRS), which has the functionality to allow the investigator to break the blind for an individual subject.

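### Baseline Ad26 immunity and region are examined only as separate one-way subgroups, so the descriptive Ad26-positive versus Ad26-negative comparison may be confounded by region and the plan cannot tell

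*SAP*

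**What the plan says.** SAP 2.4 names two immunogenicity subgroups, each on its own line: "Region (East Africa, South Africa, Thailand, USA" and "AD26 VNA at baseline (<LLOQ, >=LLOQ". SAP 2.2 plans no pooling of centres and refers back to these subgroups. SAP 6.3 specifies geometric means or medians, fold increases for the humoral assays, responder rates and graphs. It has no regression model and no table crossing the two factors. SAP 6.5 shows that a numeric Week 0 Ad26 neutralization titre is available (IC90, LLOQ 17).

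Protocol 3.1 does not restrict entry by serostatus: "Subjects will be enrolled regardless" of baseline Ad26 seropositivity. The reason, in protocol 1.1, is an earlier study of 24 subjects, 8 of them seropositive: "These data suggest that the impact of baseline Ad26 nAbs, at the titers observed in that study", was modest. The same section reports that "The T-cell responses by ELISPOT were slightly lower in the baseline Ad26 seropositive subjects". The Synopsis (Overview of Study Design) limits this evidence to what was seen "at the titers observed in that study, however regional differences are known to occur".

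Protocol section 5 has randomization "stratified by region (US, Africa, and Asia"; Ad26 serostatus is not a stratum. On regional numbers, protocol 3.1 says only: "Efforts will be made to enroll a minimum of 50 subjects per region".

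**The concern.** The regional clause in the Synopsis gives no figures, but in context it is most naturally read as saying that baseline Ad26 immunity varies by region. If so, Ad26-positive and Ad26-negative subjects will come from different mixes of regions. Any regional difference in Env response, from whatever cause, would then appear in the one-way Ad26 table as an apparent effect of vector immunity, or would hide a real one. Two one-way tables cannot separate the two factors.

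At stake is the statement the report can make about pre-existing Ad26 immunity. The evidence behind unrestricted enrolment is small and explicitly limited by titre and region, and the two regimens taken into the extension use Ad26 at all four vaccinations. A misleading descriptive result on vector immunity could be carried forward. Because region is balanced across regimens by design, such a bias would tend to run the same way in all seven active groups and could look like replication.

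**Working it through.** **The plan's own figure.** Protocol 11.2 gives 45 evaluable per group, SD 0.6 log10, two-sided 5% and 80% power for a 2.3-fold difference. The detectable difference is (1.960 + 0.842) x 0.6 x sqrt(2/45) = 0.354 log10, or 2.26-fold; power at 2.3-fold is 81.6% (normal approximation). The figure reproduces and is not in dispute. The documents give no figure for the Ad26 contrast.

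**Inputs from the documents.** SD 0.6 log10; 45 evaluable per regimen after about 10% dropout; 7 x 45 = 315 evaluable in Groups 1-7.

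**Assumed inputs.** Two equal regions; seropositivity 70/30% or 80/20%; regional Env titre ratio R of 1, 1.5 or 2, the high-seroprevalence region having the higher titre; no true Ad26 effect; equal split by serostatus.

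**Bias.** Let a and b be the shares of Ad26-positive and Ad26-negative subjects from the high-seroprevalence region. The expected crude ratio is R^(a - b). With equal regions and 80/20%, a = 0.4/(0.4 + 0.1) = 0.8 and b = 0.1/(0.1 + 0.4) = 0.2, so the bias is 0.6 x log10(R). With 70/30% it is 0.4 x log10(R).

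**Standard errors.**
- Pooled: 0.6 x sqrt(4/315) = 0.068.
- One regimen: 0.6 x sqrt(4/45) = 0.179.

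The last two columns come from a simulation (4,000 runs, SD 0.6) of the unadjusted comparison at the 5% level.

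| Seropositivity | R | Bias (log10) | Crude ratio | Bias/SE, n=315 | Bias/SE, n=45 | False positive, n=45 | False positive, n=315 |
|---|---|---|---|---|---|---|---|
| 70/30% | 1 | 0 | 1.00 | 0 | 0 | 5% | 6% |
| 70/30% | 1.5 | 0.070 | 1.18 | 1.0 | 0.4 | 7% | 17% |
| 70/30% | 2 | 0.120 | 1.32 | 1.8 | 0.7 | 10% | 42% |
| 80/20% | 1 | 0 | 1.00 | 0 | 0 | 5% | 5% |
| 80/20% | 1.5 | 0.106 | 1.28 | 1.6 | 0.6 | 9% | 34% |
| 80/20% | 2 | 0.181 | 1.52 | 2.7 | 1.0 | 17% | 75% |

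With region added to the model, the false-positive rate in these scenarios is 4.8% to 5.4%. If 75% rather than 50% of subjects come from the high-seroprevalence region, the 80/20%, R = 2 ratio falls from 1.52 to 1.41.

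**Masking.** Under the same worst case, a true halving of titre in Ad26-positive subjects would appear as 0.5 x 1.52 = 0.76.

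**Is adjustment workable?** Four regions by two Ad26 levels make 8 cells: 45/8 = 5.6 subjects per cell within a regimen, but 315/8 = 39 over the seven active regimens. Pooling is therefore needed. At 80/20% the correlation of serostatus with region is 0.6, so adjustment inflates the SE by 1/sqrt(1 - 0.36) = 1.25. The pooled ratio detectable with 80% power rises from 1.55 to 1.72.

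**The case against.** A reader might infer that the Ad26 effect is confounded with region as a matter of fact. The documents do not support that. Confounding needs both Ad26 immunity and Env response to differ by region. The protocol offers at most the first, in one clause without figures; nothing states the second. With R = 1 the bias is zero. Region is a stratification factor and an immunogenicity subgroup, which makes a regional difference plausible but does not establish it.

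A reader might also infer that regimen selection is at risk. It is not. Randomization is stratified by region, so comparisons between regimens, overall or within an Ad26 stratum, are not systematically confounded by it. The stated selection criteria are immunogenicity and safety, without Ad26 serostatus, and Groups 1 and 2 were chosen on Week 28 data. The only Ad26 objective is exploratory, and no formal hypothesis is tested.

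The larger figures also belong to a contrast pooled over seven regimens, which the SAP does not specify. Within one regimen the worst case is about 1 SE. The planned region tables would at least show whether response differs by region.

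Finally, a serostatus split is a reasonable description, and a linear term in log titre adds an assumption. If many subjects are below the LLOQ, its slope would rest largely on the same dichotomy.

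All of this stands and sets the limits of the point. It does not remove the gap: the planned tables cannot separate serostatus from region, and the data needed to do so are already collected.

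**Conclusion.** The point holds as a limited one. As planned, the descriptive Ad26-positive versus Ad26-negative comparison may be confounded by region, and the plan has no means of telling. The size is unknown from the documents. Under the assumptions listed, the spurious ratio lies between 1.00 and 1.52; in SE units it reaches about 2.7 if pooled over about 315 subjects and about 1 within a regimen of 45. It exceeds 1.00 only if both seroprevalence and response differ by region. Regimen comparisons, including the primary one, are untouched. Because SAP 6.3 applies the same approaches to extension data, the same limit applies to any Ad26 subgroup table there. This is a cheap improvement to an exploratory analysis, not a defect in the trial's main conclusion.

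**What to change.** Add a supplementary analysis to SAP 2.4 and 6.3:

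- Estimate the Ad26 effect on log10 Env titre at Week 28 and at Week 52, pooled over Groups 1-7, from a linear model with regimen, region and baseline Ad26 status. Report the adjusted ratio with its 95% CI.
- Tabulate baseline Ad26 status by region.
- As an optional sensitivity analysis, replace status by log10 baseline VNA titre, with values below the LLOQ set to LLOQ/2. The protocol's caveat concerns titre, which the two-level split discards.
- Keep the planned unadjusted tables as description.
- Align the cut-off: SAP 2.4 counts a value equal to the LLOQ as positive, while the responder definition in SAP 6.5 requires a value above it.

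The cost is one model and one table on data already collected. SAP section 1 states that the Week 96 analysis is done and will not be repeated, and that the data are unblinded, so the result must be labelled post hoc. Region-by-serostatus cells will be small (about 39 on average pooled, fewer if regions are uneven), and the adjusted estimate will be less precise than the crude one.
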